### **4.7. Interim Analyses**

An interim analysis is planned after all participants receiving SC administration in Part 1 complete the study. At that stage, all cleaned data available for participants receiving IV administration in Part 2 will also be included and analysed. The interim analysis is planned to enable a preliminary assessment of the safety and PK of this compound before final analysis is performed. The final analysis, on the other hand, will be performed after all database cleaning activities have been completed and final database lock has been declared by the data management.

All safety analyses mentioned in the SAP will be conducted as a part of interim analysis. PK analyses will use nominal sampling times and summary outputs from WinNonlin. As with the final analysis, no formal research hypothesis will be statistically tested in this study.

### **4.8. Changes to Protocol Defined Analyses**

There were no changes to the originally planned statistical analyses specified in the protocol 217901/Amendment 01 dated 03-JUN-2022.

## **5. SAMPLE SIZE DETERMINATION**

The number of participants in this study is based on clinical and practical considerations and not on a formal statistical power calculation. The total sample size of approximately 8 participants in each part is considered sufficient for the objectives of the study.

A sufficient number of participants will be enrolled to ensure approximately 8 participants complete each part of the study.

Participants who withdraw prior to study completion may be replaced.

## **6. SUPPORTING DOCUMENTATION**

### **6.1. Appendix 1 Study Population Analyses**

#### **6.1.1. Participant Disposition**

A summary of the number and percentage of participants who completed the study as well as those who prematurely withdrew from the study will be provided by study part. Reasons for study withdrawal will be summarized. Study withdrawal reasons will be listed. Participant disposition summary will be based on the Safety Analysis Set. Study analysis sets will be summarized and participants excluded from any analysis set will be listed. Screening status and reasons for screen failure will be summarized based on the screened analysis set. Reasons for screen failure will also be listed based on the screened analysis set.

#### **6.1.2. Demographic and Baseline Characteristics**

The demographic characteristics, including age at screening, sex, ethnicity, race, height, weight, and body mass index (BMI) will be summarized with descriptive statistics. Age will be treated as a continuous variable. Demographic and baseline characteristics will be listed. Demographic and baseline characteristics summary and listing will be based on the Enrolled Analysis Set. The summary will be presented by study part. A listing of race will be produced based on the enrolled set.

#### **6.1.3. Protocol Deviations**

Important (significant) protocol deviations will be summarized. The summary will be presented by study part. All protocol deviations will be listed. All inclusion/exclusion criteria deviations will be listed. Protocol deviations and inclusion/exclusion criteria deviations analyses will be based on the Enrolled Set.

#### **6.1.4. Concomitant Medications**

Concomitant medications are defined as any medications and/ or vaccines received at the time of enrolment or during the study. All concomitant medications will be listed and summarized. Concomitant medications analyses will be based on the Safety Analysis Set.

## **6.2. Appendix 2 Data Derivations Rule**

### **6.2.1. Study Period**

Screening: Screening is defined as the period between 21 days prior until 2 days prior (inclusive) to study drug administration

Check-in: Check-in is defined as the day before study drug administration

Intervention Period: Intervention period is defined as the day of study drug administration for part 1 and the time between day 1 and day 8 for part 2.

Follow-up: Follow-up is defined as the period between the day after until 167 days after (inclusive) study drug administration

### **6.2.2. Study Day**

Study day is calculated as the number of days from the date of study drug administration (study product date).

- Assessment Date = Missing → Study Day = Missing
- Assessment Date < First Study Product Administration Date → Study Day = Assessment Date – First Study Product Administration Date
- Assessment Date ≥ First Study Product Administration Date → Study Day = Assessment Date – First Study Product Administration Date + 1

### **6.2.3. Multiple measurements at One Analysis Time Point**

Not applicable

### **6.2.4. Assessment/Visit Window**

Assessment/visit windows will not be used for this study.

### **6.2.5. Handling of Partial Dates**

Element	Reporting Detail
General	

• Partial dates will be displayed as captured in participant listing displays.

• Where necessary, partial dates may be imputed for specific analysis purposes as outlined below.

• Imputed partial dates will not be used to derive study day, time to onset or duration (e.g., time to onset or duration of AEs), or elapsed time variables (e.g., time since diagnosis).

Element	Reporting Detail
Adverse Events/ Concomitant Medications/ Medical Conditions	
 
• Imputations are used for sorting in data listings.
 
• Partial dates for AE/ Concomitant Medications/ Medical Conditions recorded in the eCRF will be imputed using the following conventions: 
 
Missing start day 
 
○ If study product administration date is missing (i.e. participant did not receive study product), then set start date = 1st of month.
 
○ Else if study product administration date is not missing: 
 
▪ If month and year of start date=month and year of study product administration date then 
 
• If stop date contains a full date and stop date is earlier than study product administration date then set start date = 1st of month
 
• Else set start date = study product administration date.
 
 
 
▪ Else set start date = 1st of month.
 
 
 
 
 
Missing start day and month 
 
○ If study product administration date is missing (i.e. participant did not receive study product), then set start date = January 1.
 
○ Else if study product administration date is not missing: 
 
▪ If year of start date = year of study product administration date, then 
 
• If stop date contains a full date and stop date is earlier than study product administration date, then set start date = January 1.
 
• Else set start date = study product administration date.
 
 
 
▪ Else set start date = January 1.
 
 
 
 
 
Missing end day 
 
○ A '28/29/30/31' will be used for the day (dependent on the month and year).
 
 
 
Missing end day and month 
 
○ A '31' will be used for the day and 'Dec' will be used for the month.
 
 
 
Completely missing start/ end date 
 
○ No imputation
 
 
 
 
 

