2.3. Benefit/Risk Assessment

2.3.1. Risk Assessment

2.3.1.1. Risks of GSK3810109 and MAb Administration

Typically, the side effects of monoclonal antibodies (MAbs) are mild but may include reactions at injection site (pain, redness, bruising, swelling), fever, chills, rigors, nausea, vomiting, pain, headache, dizziness, shortness of breath, bronchospasm, hypotension, hypertension, pruritus, rash, urticaria, angioedema, diarrhea, tachycardia, or chest pain. Up to Grade 3 injection site erythema has been observed after GSK3810109 + rHuPH20 injection, and some ISRs have lasted up to 6 weeks before completely resolving. Clinical use of MAbs that are targeted to cytokines or antigens associated with human cells may be associated with an increased risk of infections ([Hansel](#), 2010); however, this is not expected to be a risk for a MAb targeted to a viral antigen.

Administration of MAbs may cause immune reactions such as acute anaphylaxis, cytokine release syndrome, serum sickness and the generation of antibodies. However, these reactions are rare and more often associated with MAb targeted to human proteins or with the use of murine or chimeric MAbs which would have a risk of human anti-mouse antibodies ([Hansel](#), 2010). In this regard, as GSK3810109 is expected to have a low risk of such side effects since it is directed against a viral antigen and is human in sequence origin.

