4. STUDY DESIGN

4.1. Overall Design

This is an open-label, single-dose study to assess the safety, tolerability, and PK of GSK3810109 administered SC with rHuPH20 or IV in healthy adult participants.

This study will comprise 3 parts:

In Part 1, approximately 8 participants will receive a single 20 mg/kg SC dose of GSK3810109 co-administered with rHuPH20 at dose of 2000 U/mL or ~28,000 U for a 70 kg participant. The participants will be admitted in the clinic on Day –1 and the study product will be administered on Day 1. The participants will remain in the clinic for approximately 8 hours for study-related procedures after study product administration and will be followed up for 24 weeks.

Safety laboratory samples will be collected throughout the study as per the SoA. The primary endpoint of ISR will be evaluated at specified time points up to Day 7; study participants will keep a diary of ISRs for 14 days after study product administration. Symptoms, maximum intensities, and durations will be reported through end of study to characterize presentation and resolution of local ISRs.

Safety review decisions and the status of the enrollment process will be shared with the Safety Review Team (SRT) in regular intervals and discussed during the monthly SRT meetings.

In Part 2, approximately 8 participants will receive a single 60 mg/kg IV dose of GSK3810109. A sentinel cohort of 2 participants will be used to mitigate the risk of unexpected AEs prior to dosing of the remaining 6 participants, who will be dosed in sequential cohorts of 2 participants each.

The sentinel cohort of these 2 participants will be admitted to the clinic on Day –1. The study product will be administered on Day 1 and participants will remain in the clinic and be monitored for 7 days after study product administration. The participants will be discharged from the clinic on Day 8 and will be followed up for 24 weeks.

Following Day 10 visit, core SRT will review the safety data (safety laboratory data, ECG, and AEs) from the sentinel cohort and may recommend continuation of the study where the next cohort of 2 participants will be dosed.

[figure not shown]

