The number and percentage of participants who have ISRs within 7 days following study product administration will be provided for parts 1 and 2. Multiple symptoms of injection site reactions will be reported as separate AEs for each reported symptom. The number and percentage of participants who have ISRs will be summarized by preferred term and by the following classifications: 'Injection Site Abscess', 'Injection Site Anesthesia', 'Injection Site Bruising', 'Injection site cellulitis', 'Injection site discoloration', 'Injection site discomfort', 'Injection site erosion', 'Injection site erythema', 'Injection site hematoma', 'Injection site hemorrhage', 'Injection site itching', 'Injection site induration', 'Injection site nodule', 'Injection site pain', 'Injection site pressure', 'Injection site soreness', 'Injection site swelling', 'Injection site tenderness', 'Injection site warmth', and 'Other'. The incidence and duration of injection site reaction AEs overall and by grade, including the time at grade, will be summarized. All ISR AEs of a participant and the corresponding length of time of events will be considered for the summary table. If there are multiple events at each grade, the length of time would be equal to the average of all event times at a grade. Participants will be included in each grade level for which they had an event.

The ISR AEs will also be summarized by each preferred term for the following variables presenting the number and percentage of participants in each category: any grade and maximum grade (1, 2, 3, 4, and 5), maximum duration (1-7, 8-14, and >14 days), outcome, and number of

events (0, 1, 2, 3, 4, 5, 6-10, 11-15, 16-20, and >20 days). In addition, an event-level summary of injection/infusion site reaction AEs by preferred term will be created which includes the following information: any grade (1, 2, 3, 4, and 5), outcome, duration, and time to onset. Duration and time to onset will be analysed as continuous variables while number and percentage will be presented for the categories of other variables.

Injection Site Reactions (ISRs)

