Serum concentration-time data will be listed for each participant and summary statistics will be calculated (i.e. arithmetic mean, 95% CI, standard deviation, CV%, median, minimum and maximum) by study part and planned sampling time. Individual serum concentrations will be plotted by treatment and nominal time on both linear and semi-logarithmic scales. Mean and median serum concentrations will be plotted by treatment and nominal time on both linear and semi-logarithmic scales.

The PK analyses will be based on (1) the PK Concentration Analysis Set for assessment and characterization of PK concentrations and (2) the PK Parameter Analysis Set for assessment and characterization of PK parameters.

*Definition of Other Secondary Endpoints (Safety and Questionnaire Data):*

Acceptance of ISRs and Individual Item Score Assessing Pain (Part 1 only): Acceptance of ISRs is assessed by the responses to Questions 17 and 18 of the PIN questionnaire. Dimension score is computed as the average of responses to Questions 17 and 18. Response to question 3 will be used to assess pain.

Bothered or Affected by Pain/Local Reactions (Part 1 only): Assessed based on the responses to each item in the PIN questionnaire and domain scores. The number and proportion of participants in each response category will be evaluated and domain scores will be summarized.

Post-Injection Pain Assessment: NRS responses will be used to assess pain after injection. The number and percentage of participants in each response level will be assessed.

Incidence and Duration of ISRs (Part 1 only): Number and proportion of patients who had ISRs will be evaluated. Duration of ISRs will be computed as the time between start and end of an ISR, inclusive of both start and end dates (end date-start date+1).

Change from baseline in Clinical laboratory assessments, ECGs, and vital sign measurements: The change from baseline will be assessed for each clinical laboratory, ECG, and vital sign assessments.

*Other Secondary Endpoints Analyses:*

All analyses for secondary safety and questionnaire data endpoints will be performed using the Safety Analysis Set. Estimands are presented in [Section 1.1](#).

Questionnaire Assessments:

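### An ISR with a partial or missing end date gets no total duration, even when visits show it lasted beyond 14 days, so Part 1 ISR duration may be understated

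*SAP*

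**What the plan says.** SAP 4.3.1 defines the endpoint: "Duration of ISRs will be computed as the time between start and end of an ISR, inclusive of both start and end dates". Two complete dates are needed.

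SAP 6.2.5 governs incomplete dates. In general, "Imputed partial dates will not be used to derive study day, time to onset or duration", and duration of AEs is among its own examples. For AEs, "Imputations are used for sorting in data listings". Under the entry "Completely missing start/ end date" nothing is imputed at all.

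SAP 4.2.2 sets the displays. Duration is summarised as a continuous variable, and each preferred term is also tabulated by "maximum duration (1-7, 8-14, and >14 days". No row for ongoing or unknown duration is listed, and no censoring rule is given. The same section says: "All ISR AEs of a participant and the corresponding length of time of events will be considered for the summary table". It also assigns the interval before a grade change to the earlier grade.

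On collection, Protocol 4.1 says "study participants will keep a diary of ISRs for 14 days after study product administration", with ISR durations to be reported up to the end of the study. Protocol 2.3.1.1 records that "some ISRs have lasted up to 6 weeks before completely resolving".

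**The concern.** A total duration exists only when both dates are complete. An ISR whose end is known only to the month, or which is still open at last contact, has none. It can therefore appear neither in the continuous total-duration summary nor in any of the three duration categories. The time spent in its last grade is lost in the same way.

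This discards information that the study holds. A reaction that began soon after dosing and is recorded as present at the Day 28 visit has lasted more than 14 days. No date has to be imputed to know that, yet the formula returns nothing.

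The loss would matter little if it struck short and long ISRs alike. In Part 1 there is reason to suspect that it may not. A short ISR ends while the participant is filling in a daily diary. The end of a long one may have to be recalled at a visit some weeks later. Long-lasting ISRs are also a known feature of this product combination, so the upper end of the duration distribution is what a reader will look for.

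**Working it through.** The documents give no figure for ISR duration and no power calculation, so there is nothing to reproduce. The check applies the SAP formula to cases.

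**1. Partial end date.** Suppose an ISR starts on 10 March and its end is recorded as April. SAP 6.2.5 would set 30 April for sorting a listing but bars that date from the duration, so no duration is derived. The possible values are bounded:
- earliest end, 1 April: 22 + 1 = 23 days
- latest end, 30 April: 51 + 1 = 52 days

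Every value consistent with the record is above 14 days.

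**2. Missing end date, presence documented.** A reaction that starts on study day *s* and is seen on day *d* has lasted at least *d* − *s* + 1 days. Onset on Day 1 and presence at Day 28 gives 28 − 1 + 1 = 28 days. If the visit is 2 days early (the Part 1 window) and onset is as late as Day 7, the minimum is still 26 − 7 + 1 = 20 days. The >14 day category is settled in both cases.

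**3. Where long ISRs end relative to recording.** The diary runs for 14 days. Part 1 visits then fall on Days 21, 28, 56 and 84 (Protocol 1.5), with windows of ±2 days at Day 28 and ±7 days from Day 56. The long ISRs that the protocol reports lasted 30 days (Protocol 2.2.1) and up to 6 weeks, or 42 days (Protocol 2.3.1.1). With onset on Day 1, they would end on about Day 30 and Day 42. Both fall between the Day 28 and Day 56 visits, when there is no diary and no scheduled visit.

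**4. Size.** Assume 8 participants with one ISR each. Short ISRs last 7 days, and long ISRs last 30 or 42 days, as in the documents. The 7-day value and the one-ISR-each pattern are assumptions.

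| ISR without a usable end date | Mean if all known (30 / 42 days) | Mean of derivable durations (30 / 42 days) | >14 day row |
|---|---|---|---|
| One long, of one | (49 + 30)/8 = 9.9 / (49 + 42)/8 = 11.4 | 49/7 = 7.0 / 7.0 | 1/8 (12.5%) to 0 |
| Two long, of two | (42 + 60)/8 = 12.8 / (42 + 84)/8 = 15.8 | 42/6 = 7.0 / 7.0 | 2/8 (25%) to 0 |
| One short, with one long fully dated | 9.9 / 11.4 | (42 + 30)/7 = 10.3 / (42 + 42)/7 = 12.0 | long ISR stays in the row |

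The median is 7 days in both long-ISR scenarios, before and after the loss. The third row shows that the direction depends on which ISR lacks a date.

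**5. Chance that there is a long ISR to lose.** The documents give no rate for ISRs over 14 days. With an assumed rate *p* per participant, the chance of at least one among 8 is 1 − (1 − *p*)^8. This gives 50% for *p* = 1/12, 77% for 2/12 and 90% for 1/4.

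**The case against.** The strongest reply is that the protocol works hard to establish when ISRs end. In Parts 1 and 3 they are events of special interest (Protocol 8.2.6), followed until they resolve or stabilise (8.2.3). Those lasting more than 7 days must be discussed with the Medical Monitor, and ISRs are photographed (8.2.7.1). Visits at Days 14, 21 and 28 bracket resolution to about a week in that stretch. Withdrawal is expected to be uncommon (7.4). In the earlier study, two Grade 3 erythema events that outlasted the diary period still have durations of 30 and 7 days (2.2.1). This stands as a reason to expect few incomplete end dates. It does not guarantee an exact end day, and it is not an analysis rule for the cases that remain.

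A second reply is that refusing to compute durations from imputed dates avoids false precision. That is correct, and the rule should stay for exact durations. A minimum duration based on a documented observation is not an imputed date.

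A third is that display details are left to the Output and Programming Specification (SAP 1), which may contain an unknown row, and that listings show partial dates as captured. A careful reader of the listings would therefore see a long ISR. The summary tables as the SAP specifies them would not show it.

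A reader might go further and infer that these ISRs are dropped from all duration results. The documents do not say so. SAP 4.2.2 says all ISR AEs will be considered, and time at an earlier grade that ends in a grade change can still be derived. The sentence does not, however, say what to do with an event whose length cannot be computed.

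**Conclusion.** The gap is real and narrow. Under SAP 4.3.1 and 6.2.5 together, an ISR with a partial or missing end date has no total duration. It is absent from the continuous total-duration summary and from the three-category table, even where documented presence already places it above 14 days.

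It would be tempting to conclude that ISR duration is biased short. The documents support only the conditional statement: it may be, if incomplete end dates fall on long ISRs. That link is a plausible inference from the 14-day diary and the Day 28 to Day 56 gap in Part 1, and nothing in the documents states it. If long ISRs have complete dates there is no downward bias, and if a short one lacks a date the mean rises.

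One affected long ISR among 8 participants moves the >14 day row by 12.5 points. Under the assumed durations it lowers the mean by 2.9 days (9.9 to 7.0) or 4.4 days (11.4 to 7.0) and leaves the median at 7. The illustration ignores multiple symptom-level ISRs per participant, which SAP 4.2.2 reports separately and averages within a grade.

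The diary argument applies to Part 1 of this SAP; Part 2 has no diary. The study is descriptive with no hypothesis test, so this is a desirable refinement rather than a serious flaw.

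**What to change.** Add one paragraph to the SAP, for ISR duration only, before the Part 1 durations are summarised at the interim analysis:

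- When the end date is partial or missing, take as a minimum duration the time from onset to the last date on which the reaction is documented present (visit, diary or photograph). If the earliest end date consistent with the partial date is later, use that instead.
- Assign a duration category only where the minimum determines it, for example >14 days. Otherwise show the ISR as undetermined.
- Flag these values as minimums, and report how many ISRs have a censored or underivable duration.
- Keep the present no-imputation rule for exact durations and for all other AEs.

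A Kaplan-Meier median is optional. With about 8 participants and several correlated symptom-level ISRs in some of them, it may add little.

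The cost is one SAP paragraph and slightly more programming, using data that are already collected. The drawback is that some durations will be shown as minimum values.

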## Trademarks

Trademarks of the GlaxoSmithKline Group of Companies	Trademarks not owned by the GlaxoSmithKline Group of Companies
Not applicable	MedDRA
	SAS

